4. Pain and symptom neuromodulation procedure.

Exercise protocol based on these 4 categories will help produce a better treatment outcome as compared to conventional Physiotherapy treatment.

If a standardized exercise program based on latest evidence designed to enable implementation into clinical practice is proved effective, the need for surgery might decrease and it will help the patients to regain the shoulder functions and improve the physical activities as well as quality of life.

Evaluation and implementation of physical activity and exercise research would be greatly facilitated if exercise programs and their components were comprehensively reported in clinical trials in a standardized way.

The proposed exercise program will provide explicit data about whether exercises are generic or individualized, the type of exercise equipment used, the exercise starting position and the program starting point, the degree of load or resistance, rules for exercise progression, motivation and adherence strategies, and exercise duration, repetitions, sets and sequence.

4. Objectives

Research Question

Is there a difference in the effectiveness of structured exercise program as compared to conventional exercise program on pain, range of motion and functions in patients with sub acromial impingement?

Hypothesis

Null Hypothesis (H0):

There will be no difference in the effectiveness of structured exercise program and conventional exercise program in the individuals with sub acromial pain.

Alternative Hypothesis (H1):

There will be significant difference in the effectiveness of structured exercise program and conventional exercise program in the individuals with sub acromial pain.

Aim and objectives

Aim- To develop and validate a structured exercise protocol and to assess its effectiveness in patients with sub-acromial impingement syndrome.

Objectives-

Phase 1:

1. To develop and validate a structured exercise program

Phase 2:

Primary Objectives: -

1. To evaluate efficacy of structured exercises on pain, range of motion and shoulder functions using Constant Murley score and Shoulder Pain and Disability Index (SPADI) and functional performance using timed functional arm and shoulder test.

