2. To compare the effectiveness of structured exercises and conventional exercises on pain, range of motion and shoulder functions using Constant Murley score and Shoulder Pain and Disability Index (SPADI) and functional performance in patients with sub acromial impingement syndrome.

5. Indicate if this is a retrospective data review

This is a prospective study

6. Study Methodology

Objective 1: Development of a structured exercise program in patients with sub acromial impingement syndrome.

1. Through the extensive literature review, the exercise program would be proposed as per the rationale of altered biomechanics and structures affected in sub acromial impingement syndrome.
2. The structured exercises program will be developed in systematic way to describe intervention, inclusive of rationale (why); materials that were used (what); procedures (what); how, where, when, how much, and by whom training will be provided, how it will be tailored and modified and how well planned it will be.
3. Structured exercise program will be formed as per the guidelines of TIDieR items which will include the name of the intervention; intervention rationale for essential elements; intervention materials and details about how to access them; description of the intervention procedures; details of intervention providers; mode of delivery of intervention; location of intervention delivery and key infrastructure; details about the number, duration, intensity, and dose of intervention sessions; details of any intervention tailoring; any intervention modifications throughout the study; and details of intervention assessment, monitoring, and level achieved.

4. Exercise protocol based on following four categories will be proposed to correct the biomechanics as per "load modification or Shoulder symptom modification process"

1. Pain and symptom neuromodulation procedure.
2. Scapular positioning techniques
3. Humeral head positioning procedures
4. Alterations to thoracic kyphosis.

This intervention will be based on shoulder kinetic control, load modification exercises and lumbopelvic stabilization with core stability exercises which is not a part of conventional exercise program for shoulder impingement syndrome patients.

Retraining exercises for scapular control

1.	Dissociate flexion to 90°.	5-10 repetitions x2.
2.	Dissociate abduction to 90°+ rotation timing	5-10 repetitions x2
3.	Dissociate medial rotation – supine arm abducted 90°	5-10 repetitions x2

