Pilot testing of structured exercise program: Pilot testing will be done on 8 patients in experimental group and 8 patients in control group.

Phase 2:

Sample size was determined using the estimates of mean and standard deviation values from literature.

Reference: Debashree Mitra, P.K Mitra et al. Effect of Specific Exercise Program and Conventional Exercise Protocol on Pain and Disability in Patients with Subacromial Impingement Syndrome. International Journal of Health Sciences and Research. 2019; 9 (8):132-139.

Using the formula

$$n = \frac{2 (Z_{\alpha} + Z_{\beta})^2 [s]^2}{d^2}$$

Where Z_{α} is the z variate of alpha error i.e. a constant with value 1.96, Z_{β} is the z variate of beta error i.e. a constant with value 0.84.

Minimally clinical difference was calculated by dividing the individual patient change score by the square root of the SEM. The RCI was considered to confer a true change when it is more than 1.96 (95 % confidence) (the z-score corresponding to the desired level of significance).

(Reference: Allen JC. Sample Size Calculation for Two Independent Groups: A Useful Rule of Thumb. Proceedings of Singapore Healthcare 2011:20(2);138-40)

Approximate estimates:

1. 80% power
2. Type I error to be 5%
3. Type II error to be 20%
4. True difference of atleast 0.31 units between the groups (SPADI)
5. Pooled standard deviation of 0.48

Substituting the values,

$$n = \frac{2 (2.8)^2 [0.48]^2}{(0.31)^2}$$

$$n = 37.31$$

Approximately 38 to 40 subjects / patients per group should complete the study at the endpoint follow up

For follow-up studies, to avoid loss by loss to follow up / attrition, kindly consider recruiting 5-25% more subjects so that even after attrition, we would be able to achieve the required minimum sample size.

Also taking into consideration the attrition to be 15%

$$n = N / (1-0.15)$$

$$n = 38$$
$$(1-0.05)$$
$$= 44.70$$

Approximately 45 subjects / patients per group need to be recruited in the present study

Assessment will be done at baseline, 3, 6, 9, and 12 weeks in both the groups, which will help to detect the changes in outcome measures at frequent intervals.

Out of the five outcome measures,

- Constant Morley part A and SPADI are patient reported scales
- T Fast is functional test
- Constant Murley and Scapulothoracic measurement are ROM assessments

15% attrition is considered while computing the sample size.

7. Study Population and Study Setting/ Location

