For a numerical continuous data following a normal distribution, inter group comparison (2 groups) will be done using t test, else a non-parametric substitute like Mann Whitney U test will be used.

Descriptive statistics like frequency (n) & percentage (%) of categorical data, mean & Standard deviation of numerical data in each group will be depicted & may be compared using chi square test or a suitable test like Fisher's exact test / McNemar test based on the data obtained.

Intra group comparisons for a numerical continuous data following a normal distribution will be done using paired t test (for 2 observations) or repeated measures ANOVA for >2 observations, else a non-parametric substitute like Wilcoxon signed rank test (for 2 observations) or Friedman's test for >2 observations will be used.

Keeping alpha error at 5% and Beta error at 20%, power at 80%, $p < 0.05$ will be considered statistically significant.

For the primary end-point, namely SPADI score after 12 weeks, and for all other outcomes, a constrained linear mixed model (cLMM) will be applied in order to compare the change from baseline to 12 weeks in experimental and control group.

Principal investigator with the help of bio stastician will be carrying out the data analysis.

16. Adverse Event Reporting

All research related incidents through the OVA/Electronic Incident Reporting System no later than 24 hours for all SAE's covered in the SOP in accordance to Policy OP 4070 REPORTING OF OCCURRENCES, VARIANCES AND ACCIDENTS.

Unanticipated Problems that are serious will be reported to HMC-IRB within 7 days of the investigator becoming aware of the event.

Any other Unanticipated Problems will be reported to HMC-IRB within 14 days of the investigator becoming aware of the event.

17. Ethical Consideration

The study will be conducted in full conformance with principles of the "Declaration of Helsinki", Good Clinical Practice (GCP) and within the laws and regulations of MoPH in Qatar

18. Sponsor, Funding & Collaborator Information

Sponsor and funding: None

This is a PhD study.

The name of the research Centre: PT School and Centre, Seth G.S.Medical College and KEM Hospital, Mumbai, Maharashtra, India

19. Dissemination of Results and Publication policy

The results will be disseminated during PhD presentations at Research Centre as well as at university. Two international publication are mandatory throughout duration of PhD as per the PhD guidelines.

20. References

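### SPADI at 12 weeks is named as primary and tested at 5%, but the effectiveness conclusion is not tied to it, and every other outcome shares the same unadjusted p < 0.05 rule

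*Combined protocol and SAP*

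**What the plan says.** Four places bear on what would count as a positive trial.

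- **Section 15 (Phase 2), threshold.** Any result with a p-value below 0.05 "will be considered statistically significant". The sentence is not limited to any outcome or visit.
- **Section 15 (Phase 2), model.** The next sentence reads "For the primary end-point, namely SPADI score after 12 weeks, and for all other outcomes, a constrained linear mixed model (cLMM) will be applied". Its stated purpose is a between-arm comparison of change over the 12 weeks. This names one primary endpoint at one time point and uses the same model for everything else.
- **Section 4, Hypothesis.** The alternative is "There will be significant difference in the effectiveness of structured exercise program and conventional exercise program in the individuals with sub acromial pain". It gives neither an endpoint nor a time.
- **Section 4, Primary Objectives, and Section 12.** The comparative primary objective begins "To compare the effectiveness of structured exercises and conventional exercises on pain, range of motion and shoulder functions using Constant Murley score" and goes on to SPADI and functional performance. Section 12 likewise places Constant-Murley, SPADI and the timed functional test side by side, unranked.

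The sample size in Section 6 is calculated on SPADI alone, at 5% type I error and 80% power. The document contains no multiplicity adjustment, no order of testing and no statement that outcomes other than SPADI are secondary, supportive or exploratory.

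**The concern.** Naming a primary endpoint protects the 5% error rate only if the trial's conclusion depends on that endpoint. Here one sentence in Section 15 singles out SPADI, while the hypotheses, the primary objectives and the outcomes section do not. Suppose SPADI shows no difference at week 12 but night pain on the VAS gives p = 0.04. A report could call that result significant under Section 15, cite it as support for the alternative hypothesis, and, because pain is among the domains named, present it as meeting a primary objective. Nothing in the text rules this out.

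At stake is the false-positive rate of the overall claim that structured exercise differs from conventional exercise, as distinct from the SPADI test itself.

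**Working it through.** **1. The plan's own figure (Section 6).** Inputs: z-values 1.96 and 0.84, difference 0.31, SD 0.48.

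n = 2 × (1.96 + 0.84)² × 0.48² / 0.31² = 2 × 7.84 × 0.2304 / 0.0961 = 37.59

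The document prints 37.31; both round up to 38 completers per group. With 15% attrition, 38 / 0.85 = 44.71, so 45 recruited per group. (The printed denominator shows 1 − 0.05, which would give 40.0, but the printed result of 44.70 matches 1 − 0.15.) The calculation uses SPADI as a single test at 5%, so the named primary endpoint carries its own 5% and no more.

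**2. How many other comparisons there are at week 12.** The plan gives no such count, so two readings bracket it.

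- *Coarse.* Section 6 refers to "Out of the five outcome measures", and Section 8 numbers five. Taking one variable for each of the four besides SPADI gives k = 4.
- *Fine.* From the Section 8 descriptions: Constant-Murley total, 1; VAS at rest, during activity and at night, 3; T-FAST tasks, 4 (hand to head, wall wash inward, wall wash outward, jug lift; no composite is defined); scapulohumeral ratio, 2 planes × 4 positions (30, 60, 90 degrees and end range) = 8. Sum: 1 + 3 + 4 + 8 = 16.
- If the ratio is taken only at 30, 60 and 90 degrees, it gives 2 × 3 = 6 variables and k = 14.

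**3. Chance of at least one p < 0.05 with no true effect.**

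Independent tests: 1 − 0.95^k.

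- k = 4: 1 − 0.8145 = 18.5%
- k = 14: 1 − 0.4877 = 51.2%
- k = 16: 1 − 0.4401 = 56.0%

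Correlated tests, for two-sided z-tests with common correlation ρ:

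1 − ∫ φ(z) [Φ((1.96 − √ρ·z)/√(1−ρ)) − Φ((−1.96 − √ρ·z)/√(1−ρ))]^k dz

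| k | ρ = 0 | 0.3 | 0.5 | 0.7 | 0.9 |
|---|---|---|---|---|---|
| 4 | 18.5% | 17.4% | 15.6% | 13.0% | 9.4% |
| 14 | 51.2% | 43.8% | 34.8% | 24.9% | 14.1% |
| 16 | 56.0% | 47.5% | 37.4% | 26.4% | 14.6% |

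The correlations are not in the documents; they are assumed and shown as a range. Every cell exceeds 5%, including the coarsest count with the highest correlation.

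**4. Visits.** The mixed-model sentence is confined to change from baseline to week 12. The t-test and Mann-Whitney sentence earlier in Section 15 names no visit, and outcomes are measured at weeks 3, 6, 9 and 12. Visit-by-visit tests are therefore neither specified nor excluded, and the table does not count them.

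**The case against.** The strongest reply is that the plan already has a single pre-specified primary endpoint and time point, and sizes the trial on it. On that view the hypothesis is general language, to be read together with Section 15, and SPADI answers it. Leaving secondary outcomes unadjusted is common when one primary is named, particularly in an unfunded PhD trial.

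Much of this stands. A reader might infer that the plan has no primary endpoint, or that it adopts a rule of declaring success on any of about 17 comparisons (SPADI plus 16). The documents do not support either reading: Section 15 names the primary, and no any-of-many decision rule is written. A reader might also set 56% against the stated 5% as though the plan's type I error were breached. The 5% in Section 6 belongs to the SPADI test and is kept. The 56% is the chance of at least one nominal finding elsewhere, and it assumes independence, which is implausible for eight readings from one shoulder or three VAS ratings from one patient. The count of 16 is itself a fine-grained reconstruction. Half of it comes from the scapulohumeral ratio, which neither the objectives nor Section 12 mentions.

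What the reply does not remove is the gap between the named endpoint and the claim. Reading the hypothesis as a SPADI hypothesis requires the reader to supply a link that the text does not make, and the primary objectives and Section 12 point the other way.

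**Conclusion.** The concern holds in a limited form. The SPADI test at week 12 is sound as a 5% test. The defect is that the effectiveness conclusion is not bound to it, while all other outcomes share its threshold without adjustment or label.

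With no true difference, the chance of a nominally significant non-SPADI result at week 12 is about 9% to 19% for four variables and about 15% to 56% for 16. Each range runs from a common correlation of 0.9 down to independence. Both the number of variables and the correlations are assumptions; the direction of the conclusion does not depend on them. This deserves correction before results are seen, but it does not invalidate the primary analysis.

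**What to change.** Three wording changes:

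1. In Section 4, word H0, H1 and the comparative primary objective on the arm difference in SPADI change from baseline to week 12.
2. In Section 15, state that only this test, at p < 0.05, supports the conclusion that the programmes differ in effectiveness.
3. In Sections 12 and 15, label all other outcomes, and all other visits, as secondary. Report them as arm differences with 95% confidence intervals, described as supportive and unadjusted for multiplicity.

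No extra patients are needed: the requirement stays at 38 completers and 45 recruited per group. Splitting alpha across outcomes would be costly by comparison. A Bonferroni split over 17 tests (0.05 / 17 = 0.0029) would cut SPADI power at 38 per group from 80.4% to 43.7% and require 70 completers (83 recruited) per group. A formal testing sequence for the secondary outcomes is optional and not required here. The only cost of the change is that secondary findings carry weaker wording.

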Evaluation of the participant will be done at the baseline using Constant Murley Score, shoulder pain and disability Index (SPADI). Shoulder range of motion, shoulder muscles extensibility will be assessed and scapulothoracic ratio will be calculated and documented. T-FAST test will be conducted to score the patients functional performance.

specified timeframes for phase 1 and phase 2

Sr. No.	Task	Timeline
1.	Phase 1: developing and validating the structured exercise program	6 months
2.	Pilot phase	6 months

3.	Phase 2: RCT, implementation of exercise program	2 years
----	--	---------

Outcome measures:

1. Constant–Murley Score

This score is a shoulder-specific assessment tool containing objective measures (range of movement and shoulder strength) and subjective measures (activity of daily living and pain). The maximum is 100 points and indicates excellent shoulder function.

The CMS scale assesses four aspects related to shoulder pathology; two subjective: pain and activities of daily living (ADL) and two objectives: range of motion (ROM) and strength. The subjective components can receive up to 35 points and the objective 65, resulting in a possible maximum total score of 100 points (best function). Pain and ADL are answered by the patient; ROM and strength require a physical evaluation and are answered by the physiotherapist.

Questions and measurements are standardized according to the original description by Constant and Murley.

2. Pain perception

The visual analogue scale (VAS; 0–10) is used to assess the patient’s perceived pain intensity at rest, during arm activity and at night during the previous 24 hours at each follow-up.

3. Shoulder Pain and Disability Index (SPADI)

The Shoulder Pain and Disability Index (SPADI) is a self-administered questionnaire that consists of two dimensions, one for pain and the other for functional activities. The pain dimension consists of five questions regarding the severity of an individual's pain. Functional activities are assessed with eight questions designed to measure the degree of difficulty an individual has with various activities of daily living that require upper-extremity use. The SPADI takes 5 to 10 minutes for a patient to complete and is the only reliable and valid region-specific measure for the shoulder.

4. Timed Functional Arm and Shoulder Test

Description of the Timed Functional Arm and Shoulder Test.

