Flexibility and stretching

Continue all stretching and range-of-motion exercises

L-Bar: External rotation /internal rotation at 90° abduction

Continue capsular stretch

Maintain/increase posterior/inferior flexibility

Strengthening exercises (5-10 repetitions x2.)

- Establish patient on the fundamental shoulder exercises
- Tubing external rotation /internal rotation
- Lateral raises to 90° dumbbell
- Full can dumbbell to 90°
- Side lying External rotation
- Prone horizontal abduction
- Prone extension
- Wall slides
- Biceps/triceps
- Scapular neuromuscular control drills

Guideline for progression to phase 4

- Full, nonpainful range of motion
- No pain or tenderness

Strength test fulfills criteria

- Satisfactory clinical examination

Return to activity phase

Goals

Unrestricted, symptom-free activity

The exercises to be performed at the PT clinic 2 times a week combined with home exercises twice daily.

Any dropouts or participants lost to follow-up will be mentioned with appropriate reasoning.

At the end of the study the data will be collected, coded and tabulated using descriptive and inferential statistics. All analysis will be done using SPSS for Windows (Version 16).

9. Study Duration and Timelines

Total duration of study: 3 years

The treatment protocol will be given for two days per week for twelve weeks.

Each treatment session will be for 45 mins.

Assessment will be done at baseline, 3, 6, 9, and 12 weeks in both the groups.

The treatment protocol will be participant specific and progression will be made according to the participant's performance.

specified timeframes for phase 1 and phase 2

Sr. No.	Task	Timeline
1.	Phase 1: developing and validating the structured exercise program	6 months
2.	Pilot phase	6 months
3.	Phase 2: RCT, implementation of exercise program	18 months

Timeline for the entire study

Sr. No.	Task	Timeline
2.	Related Literature Search	September 2022
6.	Institutional Ethical Committee Approval	October-December 2022
9.	Data Collection Post MRC Approval	February 2023-February 2025
10.	Data Presentation and Analysis	March 2025
11.	Writing Discussion and Conclusion	June 2025
12.	Preparing manuscript and publication	August 2025

10. Informed Consent

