The patients who are endorsed in physiotherapy OPD will be approached to consider being a research subjects, Principal investigator will be taking informed consent from the patients. Participants can take 24-72 hours to decide on participation in research. Subjects will be screened for eligibility criteria as per the inclusion and exclusion criteria, Subjects will be enrolled in the study through simple random method.

11. Risk

Potential risks associated with this study are none or very minimal. The time required is 45 minutes is the only discomfort which will be having throughout the study. There is possibility of increase in shoulder pain after exercises which will be managed with pain relieving electrotherapeutic modalities.

The therapist will always be in the vicinity to prevent and treat the same.

12. Outcomes

The effect of structured exercises on pain, range of motion and shoulder functions using Constant Murley score and Shoulder Pain and Disability Index (SPADI) and functional performance using timed functional arm and shoulder test will be tested and compared with conventional exercise program.

13. Data Collection, Management & Confidentiality

a) Indicate below HOW study data will be collected for the proposed research.

√ Study Forms Study Database Study Web-Based/App Other

A standardized data collection tool will be developed. Variables will be designated to measure the pre specified outcomes.

The subject data will be coded by Alphanumeric notations. The subject name and the number will be coded and the subject identifier will be kept locked in the drawer. Subject identifiers- Name, HC number and Date of Birth (DOB) will not be included in the data collection sheet. Subject identifiers will be logged in the subject code and identification list.

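### The plan foresees increased shoulder pain after exercise but specifies no count of patients whose pain worsens and no harms table by arm, so early worsening, or worsening in a minority, need not be reported.

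*Combined protocol and SAP*

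**What the plan says.** - **Foreseen harm (Section 11, Risk).** "There is possibility of increase in shoulder pain after exercises which will be managed with pain relieving electrotherapeutic modalities". No rule is given for defining, recording or counting such an increase. The same section describes the study's risks as absent or very small.
- **Reporting (Section 16, Adverse Event Reporting).** Research-related incidents and SAEs go to the institution's incident system and serious unanticipated problems go to the IRB. For the rest: "Any other Unanticipated Problems will be reported to HMC-IRB within 14 days of the investigator becoming aware of the event". No tabulation by arm is mentioned.
- **Pain data (Section 8, Outcome measures).** For SPADI, "The pain dimension consists of five questions regarding the severity of an individual's pain". The VAS covers "perceived pain intensity at rest, during arm activity and at night during the previous 24 hours at each follow-up".
- **Schedule (Sections 6 and 9).** "Assessment will be done at baseline, 3, 6, 9, and 12 weeks in both the groups". The sample size text in Section 6 gives the purpose of the repeated assessments: "which will help to detect the changes in outcome measures at frequent intervals".
- **Analysis (Section 15, Phase 2).** The model named for SPADI and every remaining measure is this: "a constrained linear mixed model (cLMM) will be applied in order to compare the change from baseline to 12 weeks in experimental and control group". For normally distributed numerical data, "inter group comparison (2 groups) will be done using t test, else a non-parametric substitute like Mann Whitney U test will be used". Section 15 also lists group means and SDs, within-group tests over repeated observations, and chi-square or Fisher tests for categorical data. None of these names a worsening variable.

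**The concern.** The protocol anticipates that exercise may make pain worse, and then sets out nothing that would show how often this happened in each arm. A pain increase that the protocol itself expects is not clearly an SAE or an unanticipated problem, so it may not reach the Section 16 stream. If it does, that stream ends with the institution and the IRB, not with a comparison of the arms.

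The listed analyses of pain scores do not fill the gap. A mean or rank comparison does not say how many patients got worse. A contrast at week 12 does not show worsening at weeks 3 to 9 that has since settled. Reporting dropouts with reasons misses patients who get worse and stay in.

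The trial is meant to support uptake of a new exercise programme. Followed as written, it could report a benefit on mean SPADI and call the risk minimal without having compared how often each programme made pain worse.

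**Working it through.** **1. Denominators, from the plan's own calculation (Section 6).** Inputs: 2.8 for the summed z values, SD 0.48, difference 0.31.

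n = 2 × 2.8² × 0.48² / 0.31² = 2 × 7.84 × 0.2304 / 0.0961 = 37.59.

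The protocol prints 37.31; both round up to 38. With 15% attrition, 38 / 0.85 = 44.7, so 45 recruited. (The printed divisor of 1 − 0.05 would give 40.0 and is a slip; the result matches 15%.) A harms table would therefore rest on 45 per arm at most and about 38 completers at week 12.

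**2. What each planned analysis can show about worsening.**

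| Planned item | Compares arms? | Visit fixed? | Counts patients who worsen? |
|---|---|---|---|
| Constrained mixed model | Yes | Week 12 | No |
| t or Mann-Whitney test | Yes | None named | No |
| Repeated measures ANOVA or Friedman test | No, within arm | Over visits | No |
| Group means and SDs | Side by side | None named | No |
| Chi-square or Fisher test | Possibly | None named | No worsening variable defined |
| Section 16 reports | No | n/a | No |

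**3. How a mean can hide worsening (assumed values).** Let the control arm's mean VAS change be −2.0. Let 20% of the structured arm worsen by 2.0 and the other 80% improve by x. The arm means are equal when 0.8x − 0.2 × 2.0 = 2.0, so x = 3.0. An improvement of 3 points in four fifths of the arm hides worsening in one fifth, and the mean contrast is zero. At 10% worsening x = 2.4; at 30% x = 3.7.

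**4. Precision of a worsening table (assumed 20% v 5%).** Half-width = 1.96 × √(0.20 × 0.80/n + 0.05 × 0.95/n). The one-sided 95% upper bound when nobody worsens is 1 − 0.05^(1/n). Power is for a two-sided Fisher exact test at 5%, summed over all possible tables.

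| | 45 per arm | 38 per arm |
|---|---|---|
| Risk difference | 15 points | 15 points |
| 95% half-width | 13.3 points | 14.5 points |
| Upper bound, 0 events | 6.4% | 7.6% |
| Fisher exact power | 48% | 38% |

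The table can estimate but cannot serve as a test. Even with no events it supports a bounded statement about risk in each arm.

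**5. Limits of the proxy.** The VAS looks back 24 hours at four follow-up visits, about 4 of 84 days (4.8%). Scores every three weeks are not a record of pain after each session.

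**The case against.** A reader might infer that pain scores are compared only as mean change to week 12, and that early worsening would certainly go unreported. The documents do not support that. Section 15 also lists between-group t or Mann-Whitney tests without naming a visit, and group means and SDs. Section 6 says the frequent assessments are there to detect change. A comparison at week 3 is neither required nor ruled out, so an early worsening of the mean could appear. Unequal spread between arms might also show in the SDs, although the plan does not say whether these are SDs of scores or of change. Nor do the documents raise any particular subgroup; the point concerns a minority of patients within an arm.

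Three further objections stand in part.

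- The named harm is pain after exercise, and visit scores are only a proxy for it. The gap is therefore partly one of data collection, which a new table does not close.
- The collection form cannot be checked, because Appendix 1 is listed by title only. The list of baseline measures in Section 8 does not name the VAS, so a VAS baseline may not exist.
- Section 16 opens by referring to all research-related incidents, in an incomplete sentence. Some pain increases may be reported by that route, but still without comparison by arm.

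None of this supplies a count of patients who worsen, or a harms table by arm.

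**Conclusion.** The point holds in a limited form. The plan names increased shoulder pain as a possible consequence of exercise and specifies neither a count of patients who worsen nor any comparison of harm by arm. The only between-arm contrast fixed in time is mean change to week 12. The other tests could reveal an early shift in the mean, but nothing obliges them to, and none would show worsening in a minority.

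The size of the problem is unknown. The documents give no worsening rate, and every rate used above is an assumption. The denominators rest on the plan's 45 recruited and about 38 completers per arm. The conclusion also reads the assessment schedule as including SPADI at every visit. The sample size and the primary analysis are unaffected. This is an inexpensive improvement to reporting, not a flaw in the main comparison.

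**What to change.** Add one paragraph and one table to Section 15, labelled as descriptive safety:

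- By arm, at weeks 3, 6, 9 and 12 and at any visit, give n (%) of patients whose SPADI pain dimension is worse than their own baseline by more than a margin. The investigators fix the margin before any unblinded data are seen, so that measurement noise is not counted as harm.
- Give the between-arm risk difference with its 95% CI at each of these points, and make no p-value claim.
- Count withdrawals due to increased pain as worsened.
- Present the VAS in the same way only where a baseline value exists.
- State that three-weekly scores are a proxy that misses flares between visits.
- Base the report's statement on risk on this table.

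Cost: no new visits, staff or measurements. The downside is wide intervals, about 13 to 14.5 points either side under the assumed rates. Logging pain increases after sessions in both arms would come closer to the harm named in Section 11, but it adds data collection and goes beyond this change.
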